5. CONCEPTUAL FRAMEWORK AND OPERATIONALIZATION

Figure 1 shows how project activities (inputs) will lead to outputs and result in outcomes as well as the potential impact of the planned activities. The model shows the combined activities planned within study 1 and study 2.

[figure not shown]

Figure 1: Logic model for the CIFF/IAF programme that includes the two studies presented in this protocol

The objectives of the programme intervention and the indicators to assess achievement of these objectives are shown in Table 1.

Table 1: Objectives and corresponding key indicators

Level of data	Hypothesis	Indicators	Proposed studies
Purpose 1: To assess the effect of the 1AF intervention package on birth outcomes, anemia, micronutrient deficiencies, stunting, and morbidity in mothers and their young children			
Impact	Decreased stunting in children receiving the intervention package (or parts thereof)	
 • Change in length-for-age z scores (LAZ) • Percentage of children whose LAZ is below -2 standard deviations from the median of the WHO Child Growth Standard 	• Study 1&2
Impact	Reduced prevalence of anemia and micronutrient deficiencies in children receiving the intervention package	
 • Change in proportion with anaemia • Change in haemoglobin concentration • Change in retinol binding protein concentration (i.e. vitamin A status) • Change in concentration of serum ferritin and soluble transferrin receptor (i.e. iron status) 	• Study 1
Impact	Increased birth weight of children from mothers having received the intervention package during the pregnancy	
 • Change in birth weight 	• Study 1
Outcome	Reduced prevalence (or incidence) in diarrheal disease in infants and young children receiving the intervention package	
 • Age- and sex-specific morbidity rates with a focus on diarrhoea 	• Study 1
Purpose 2: To identify and assess the conceptual and operational factors at the different stages of the intervention package that may have affected the outcome			
Outcome	Increased intake of nutritional products among pregnant and lactating women and children	
 • Consumption of adequately formulated nutritional products in the period preceding data collection • Monitoring of type, frequency and quantity of adequate nutritional products 	• Study 1&2
Outcome	Increased dietary diversity among pregnant and lactating women	
 • FANTA/FAO minimum Dietary Diversity-Women 	• Study 1
Outcome	Increased adherence to adequate child feeding practices	
 • Prevalence of early initiation of breastfeeding • Prevalence of exclusive breastfeeding • Duration of exclusive breastfeeding • WHO suite of IYCF (Infant and Young Child Feeding) indicators of dietary diversity, frequency, and adequacy 	
 • Study 1 • Study 1&2
Outcome	Improved WASH practices	
 • Ability to identify five critical times for handwashing • Proportion of households with soap and water available 	• Study 1&2
Outcome	Improved access to and availability of nutritionally adequate products for pregnant and lactating women and children	
 • Access to nutritionally adequate foods • Affordability of such products as a function of the socio-economic status of the respondent 	• Study 1&2

Output	Increased knowledge and awareness of the importance of adequate antenatal and child feeding practices and care	
 • Ability to differentiate between facts and myths on antenatal and child feeding practices and care • Knowledge of new information gathered on child feeding practices and formulated nutritional products for pregnant and lactating women and children • Knowledge of the risks for not having adequate antenatal and child feeding practices and care • Awareness of sources of information for antenatal and child feeding practices 	• Study 1&2
Purpose 3: To determine unintended consequences of the interventions			
Outcome	Inappropriate use of nutritionally adequate products	• Percentage of children less than 6 months of age not exclusively breastfed due to provision of complementary foods before 6 months of age	• Study 1&2
Impact	Increase in the prevalence of overweight and obesity	• Percentage increase in the proportion of children whose WHZ (weight for height z-score) is above +2 and +3 standard deviations from the median of the WHO Child Growth Standard	• Study 1&2

Several factors may influence our results, which we will take into account during data analysis. The following parameters assessed at baseline have been defined as independent variables to potentially influence the outcome at delivery and study end of **study 1**:

- maternal height
- maternal BMI (body mass index)
- maternal age
- maternal education
- gestational age at enrolment
- parity
- time interval from prior birth
- household socio-economic status
- household food insecurity
- site

The following additional parameters assessed at round 3 (delivery) have been defined as independent variables for study endpoint outcomes:

- child sex
- mode of delivery

The following parameters assessed at baseline have been defined as independent variables to potentially influence the outcome at round 2 and 3 of **study 2**:

- maternal age
- maternal education
- parity
- time interval from prior birth
- child sex
- household socio-economic status
- household food insecurity
- whether cluster received health insurance (other study taking place in the same district)
- site

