pregnancy resulting in increased weight, length and head circumference at birth as compared to women receiving iron and folic acid supplements [19,20]. One study, conducted in Bangladesh, has demonstrated the positive effect of LNS provided during pregnancy and infancy on child linear growth and head circumference [21]. There is clear evidence on the efficacy and effectiveness of the use of MNPs with respect to increased micronutrient status, reduction of anaemia prevalence and improved growth in most settings [22,23]. However, in some settings simultaneous prevention of common diseases (e.g. malaria, other infectious diseases) might be needed to see an effect as some studies in malaria-endemic areas using fortified products have demonstrated limited efficacy [24-26].

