6. HYPOTHESIS/RESEARCH QUESTIONS

Study 1 hypothesis: Linear growth in children during their first 24 months of life will improve after the provision of agricultural services, nutritionally enhanced and WASH products as well as nutrition and WASH training over the period of the 1,000 days window of opportunity when compared to the control group provided only with agricultural services.

Study 2 hypothesis: Linear growth in children between 6-59 months of age will improve after the provision of agricultural services, nutritionally enhanced and WASH products and diversified crops as well as nutrition and WASH training over the period of 2 years when compared to the control group provided only with agricultural services.

Table 2 below indicates the expected direction of relationship between the independent variables and the primary outcome (length at 24 mo of age in study 1 and length after 2 years of intervention in study 2).

Table 2: Expected direction of relationship between independent variables and primary outcome (linear growth)

Independent variable	Direction of relationship	Study
Maternal height	Positive	1
Maternal BMI	Positive unless overweight/obese	1
Maternal age	Negative in youngest as rather inexperienced and physiologically less ready	1&2
Maternal education	Positive	1&2
Gestational age at enrolment	Younger gestational age is positive as duration of intervention is longer	1
Parity	Negative (multiparous higher risk of stunting)	1&2
Time interval from prior birth	Longer interval is positive	1&2
Household socio-economic status	Positive	1&2
Household food insecurity	Negative	1&2
Health insurance intervention	Positive if people go more often to health centres	2
Site	Direction is not clear	1&2
Child sex	Positive with female sex	1&2
Mode of delivery	Caesarean section negative	1

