We anticipate recruiting 1,200 (600 in each group) pregnant women into the study (see section 11.2 for sample size calculation); this is expected to yield a sufficiently large sample of children later in the study. Women will be recruited from 120 clusters (randomly assigned to intervention or control) that will be drawn from from Kimilili and Webuye districts in Bungoma County in Western Province of Kenya.

The communities will be informed about the study in village meetings by CHVs and by conducting outreach within their catchment area to identify pregnant women. Pregnant women will then be screened by 1AF enumerators. During **screening**, a few questions on health status and pregnancy will be asked. If the woman is prior or equal to 20 weeks of gestation (according to last menstrual period), has no visible severe disease and no allergy to peanuts or milk products, and confirms anticipated residence in the area for the coming 30 months, written informed consent for her and her offspring will be sought from her. She will then be asked to provide a urine sample to confirm pregnancy and she will be enrolled if pregnancy is confirmed. Following the screening, 5 assessment rounds (baseline and 4 follow-up assessments during the intervention) will be conducted at the participant's homes (rounds 1-3) or at a central place (rounds 4 and 5) within walking distance from their homes (Figure 2). Assessment round 3 (immediately) after delivery will be conducted as home visits or clinic visits in case of delivery at a clinic. Details of assessment procedures for each round are illustrated in (Figure 3).

Round 1 (Enrolment, ≤ 20 wk of gestation):

On the day of enrolment the round 1 assessment will be done. As part of this, the following information will be collected: household demographics and characteristics, maternal education; knowledge, attitude and practices (KAP) of specific dietary and nutrition practices during pregnancy; individual dietary diversity; antenatal care; WASH practices; height, weight and mid-upper arm circumference; maternal haemoglobin concentration and malaria parasitaemia from a capillary blood sample. After round 1, participants randomly allocated to the intervention group will start receiving the intervention package.

Round 2 (Gestational age of 34 ± 1 wk):

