In round 2, interview questions related to diet and nutrition KAP during pregnancy, dietary diversity, antenatal care, and WASH will be asked. Additionally, MUAC (mid-upper arm circumference) will be measured and a capillary blood sample for measurement of haemoglobin concentration, malaria parasitaemia and micronutrient status will be provided.

Round 3 (Within 24-48 hours after delivery):

The mother-child pair will be visited within 24-48 hours after delivery. The following information will be recorded: delivery date and time, delivery method, recent antenatal care, and early initiation of breastfeeding. The mother will be assessed for MUAC but no blood sampling will be conducted. For the newborn, head circumference, birth weight and birth length, and haemoglobin concentration (from a heelprick) will be measured.

Round 4 (At 6.5 mo ± 1 mo of age of offspring):

This assessment will be conducted when the child turns 6.5 months old. Breastfeeding and other infant and young child feeding indicators, child morbidity, maternal dietary diversity, postnatal care, and WASH information will be gathered. In mothers, MUAC and weight will be measured and haemoglobin concentration and malaria parasitaemia from a capillary sample will be assessed. In

children, length, weight and head circumference will be measured and a capillary blood sample for haemoglobin concentration, malaria parasitaemia and micronutrient status will be provided.

Round 5 (At 24 ± 1mo of age of offspring):

This assessment will be conducted when the child turns 24 months old. Questionnaire-based information on child feeding, child dietary diversity, child morbidity and WASH will be collected. As in round 4, child length, weight and head circumference will be measured and a fingerprick blood sample will be provided for the measurement of haemoglobin concentration, malaria parasitaemia, and micronutrient status. No maternal biomarkers will be collected at this point.

As part of the monthly visits to the participants' households, the CHV will also collect data on intervention adherence and recent morbidity.

[figure not shown]

Figure 2: Timing of assessment rounds for study 1.

[figure not shown]

Figure 3: Detailed procedures for each assessment round in study 1

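### Study 1 lists mode of delivery, recorded after the package has begun and open to its influence, among the covariates for 24-month outcomes and nowhere keeps it out of the arm comparison

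*Protocol*

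**What the plan says.** Section 5 introduces its covariate lists with a commitment: "Several factors may influence our results, which we will take into account during data analysis". For Study 1 it gives a list measured at baseline and then continues: "The following additional parameters assessed at round 3 (delivery) have been defined as independent variables for study endpoint outcomes". The two items that follow are child sex and "mode of delivery". Table 2 in section 6 gives the expected relation of each independent variable to the primary outcome. For mode of delivery in Study 1 the entry is "Caesarean section negative".

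On timing, section 7.1 says of enrolment, at 20 weeks of gestation or earlier: "After round 1, participants randomly allocated to the intervention group will start receiving the intervention package". Round 3, within 24-48 hours after delivery, records "delivery date and time, delivery method, recent antenatal care, and early initiation of breastfeeding".

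Section 9.2 declares an intention-to-treat comparison. Section 9.2.1 compares mean change in LAZ between arms by linear regression and names socio-economic status, sex and age as the minimum covariates. It neither names nor excludes mode of delivery, and refers details to the statistical analysis plan.

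**The concern.** Mode of delivery lies between the start of the package and the 24-month endpoint. The protocol itself supplies two routes by which the package could change it.

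- **Size at birth.** Table 1 hypothesises higher birth weight in the intervention arm. Section 3 cites two earlier trials of LNS in "pregnancy resulting in increased weight, length and head circumference at birth as compared to women receiving iron and folic acid supplements".
- **Use of care.** Only the intervention arm gets the antenatal care messages and the training modules for pregnant women.

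A regression that includes a variable affected by treatment no longer estimates the total effect of being randomised to the package. It removes whatever part of the effect passes through delivery mode. It also brings in any unmeasured factor that influences both caesarean section and growth: among children with the same delivery mode, the arms are no longer balanced on that factor. What is at stake is the meaning of the adjusted arm effect on the primary outcome.

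Child sex is also recorded at round 3, but it is fixed at conception and raises no such difficulty.

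**Working it through.** **1. Timing.** A woman enrolled at the 20-week limit who delivers at 37 weeks has at most 37 - 20 = 17 weeks of exposure; earlier enrolment or later delivery gives more. Mode of delivery is therefore observed after treatment has begun.

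**2. Which model receives it.** Section 5 and Table 2 attach mode of delivery to endpoint outcomes and to the primary outcome. Section 9.2.1 sets only a minimum covariate list. Nothing in the protocol confines mode of delivery to an exploratory model.

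**3. Yardstick from the plan's own figures (section 7.2).** Retention = 0.95 × 0.80 × 0.95 × 0.75 = 0.5415, a loss of 45.85%, which agrees with the 46% in section 7.3.3. Effective number per arm = 600 × 0.5415 / 1.3 = 249.9. Standard error of the arm difference = √(2/249.9) = 0.089 SD. Detectable effect at 80% power, two-sided 0.05 = (1.960 + 0.842) × 0.089 = 0.251 SD. The protocol states 0.26, which is slightly cautious (power at 0.26 is 82.8%) and is not in dispute here.

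**4. Size of the shift.** In a linear model with arm and delivery mode,

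adjusted effect - total effect = -(fitted caesarean coefficient) × (intervention minus control caesarean proportion).

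The protocol gives neither quantity, so both are assumed: a coefficient of 0.1 to 0.4 SD in absolute value and an arm difference of 2 to 5 percentage points in either direction.

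- Smallest: 0.1 × 0.02 = 0.002 SD, or 0.002/0.26 = 0.8% of the stated detectable effect.
- Largest: 0.4 × 0.05 = 0.02 SD, or 0.02/0.26 = 7.7%; in standard errors, 0.02/0.089 = 0.22.
- No arm difference in caesarean section: zero.

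These are SDs of the change in LAZ. Reading them as LAZ units assumes that this SD is 1.

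**5. Sign.** A simulation of 2,000,000 children used a direct arm effect of 0.26 and a caesarean proportion near 10% in controls before any unmeasured factor is added. OR is odds ratio; the common cause raises both caesarean section and growth (0.5 SD of outcome per SD).

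| Arm on caesarean (OR) | Common cause on caesarean (OR per SD) | Caesarean effect on outcome | Total | Adjusted | Shift |
|---|---|---|---|---|---|
| 1.0 | none | -0.2 | 0.259 | 0.259 | 0 |
| 1.6 | none | -0.2 | 0.251 | 0.261 | +0.010 |
| 1.6 | 2 | -0.2 | 0.248 | 0.242 | -0.007 |
| 2.0 | 3 | -0.3 | 0.234 | 0.220 | -0.015 |
| 0.62 | 2 | -0.2 | 0.268 | 0.273 | +0.005 |

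The sign turns on the unmeasured factor. In the third row the caesarean proportions are 0.117 and 0.171, a difference of 0.054, so the fitted coefficient is 0.0068/0.054 = +0.126 although the causal effect is -0.2. The common cause has added 0.326.

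A common cause of the same strength that lowers growth would give a coefficient of -0.2 - 0.326 = -0.526 and a shift of 0.526 × 0.054 = +0.028 SD. The same reversal in the fourth row (proportions 0.140 and 0.228, difference 0.088) gives 0.0146/0.088 = +0.166, then -0.3 - 0.466 = -0.766, and a shift of 0.766 × 0.088 = +0.067 SD. That row is deliberately extreme. The range in step 4 is therefore not a ceiling; it holds for fitted coefficients up to 0.4 and arm differences up to 5 points.

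**The case against.** The strongest reply is that no analysis section says the primary model will include mode of delivery. Section 5 is a conceptual framework, it names no model, and its variables are described only as potential influences. Table 2 can be read as a table of determinants of growth. Its reason for gestational age at enrolment, a longer duration of intervention, applies only to the intervention arm and is not a reason to adjust for a confounder. Section 4.3 sets a secondary objective of studying factors that may have affected the outcome, and mode of delivery has a proper place there.

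Much of this stands. A reader might infer that the primary model is already fixed to adjust for mode of delivery. Section 9.2.1 does not support that. A reader might also infer that the protocol predicts larger heads in this trial. It does not: Table 1 names birth weight only, and the head circumference result belongs to earlier trials with a different comparator. Nor does the Table 2 row have to go.

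What the reply does not remove is the commitment in section 5 to take the listed factors into account, the attachment of mode of delivery to endpoint outcomes, and an open covariate list in section 9.2.1. Someone building the model from this protocol could include it and be following the text. The point concerns what the protocol states, not detail it leaves to the analysis plan.

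A second reply is that the shift is too small to change a conclusion. Under the main assumptions that is probably right, and it limits the priority. It does not make the adjustment useful, because the sign is unknown and the shift cannot be called conservative.

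**Conclusion.** The point holds in limited form. The protocol places a post-randomisation variable, plausibly affected by the package, among the adjustment variables for the 24-month comparison in Study 1, and nothing in it keeps that variable out of the arm comparison. Adjusting for it would estimate something other than the intention-to-treat effect.

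The size is roughly 0.002 to 0.02 SD, at most about a fifth of a standard error. This assumes a 2 to 5 point arm difference in caesarean section and a fitted coefficient of 0.1 to 0.4 SD. It could be larger with a strong unmeasured cause that raises caesarean section and lowers growth. The documents do not support the stronger inference that the randomised effect is lost or that the trial's conclusion would change. Priority is low to moderate.

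**What to change.** In section 5, take mode of delivery out of the covariates for the arm comparison and state that this comparison adjusts only for round 1 covariates and child sex. Add the same limit to section 9.2.1 so that the open list cannot readmit it. Report mode of delivery by arm as an outcome. If it is wanted as an explanatory variable, use it only in an analysis labelled as an exploratory determinants or mediation analysis; the Table 2 row may stay if it carries that label.

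The cost is a sentence or two of text. Data collection, sample size, power and alpha are unchanged, and the loss of precision should be negligible. The change should be made before the arms are compared on endpoint data.

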6. HYPOTHESIS/RESEARCH QUESTIONS

Study 1 hypothesis: Linear growth in children during their first 24 months of life will improve after the provision of agricultural services, nutritionally enhanced and WASH products as well as nutrition and WASH training over the period of the 1,000 days window of opportunity when compared to the control group provided only with agricultural services.

Study 2 hypothesis: Linear growth in children between 6-59 months of age will improve after the provision of agricultural services, nutritionally enhanced and WASH products and diversified crops as well as nutrition and WASH training over the period of 2 years when compared to the control group provided only with agricultural services.

Table 2 below indicates the expected direction of relationship between the independent variables and the primary outcome (length at 24 mo of age in study 1 and length after 2 years of intervention in study 2).

Table 2: Expected direction of relationship between independent variables and primary outcome (linear growth)

Independent variable	Direction of relationship	Study
Maternal height	Positive	1
Maternal BMI	Positive unless overweight/obese	1
Maternal age	Negative in youngest as rather inexperienced and physiologically less ready	1&2
Maternal education	Positive	1&2
Gestational age at enrolment	Younger gestational age is positive as duration of intervention is longer	1
Parity	Negative (multiparous higher risk of stunting)	1&2
Time interval from prior birth	Longer interval is positive	1&2
Household socio-economic status	Positive	1&2
Household food insecurity	Negative	1&2
Health insurance intervention	Positive if people go more often to health centres	2
Site	Direction is not clear	1&2
Child sex	Positive with female sex	1&2
Mode of delivery	Caesarean section negative	1

7. STUDY DESIGN AND SAMPLING STRATEGY

7.1 Study design and sampling procedures

Study 1:

General study design: Study 1 is a cluster-randomized, parallel-group, prospective, follow-up effectiveness study over a period of 1000 days comparing 2 groups:

- a) Intervention group: **Pregnant women** will be given LNS (1 sachet/day), raw eggs (2/day), and an anthelmintic drug (albendazole) in the second trimester of pregnancy, as well as soap and chlorine solution for the woman and the household. After delivery these products will be continued until the child reaches 6 months of age. Thereafter, LNS and eggs for mothers and anthelmintic drugs will be discontinued and instead, the **child** will receive LNS (1 sachet/day), one egg/day and Oral Rehydration Salts (ORS) along with zinc tablets (20 mg/day) for treatment in case of acute diarrhoea. These products will be given until the child reaches 2 years of age. The products will be accompanied by life stage-appropriate nutrition and WASH trainings (pregnancy, lactation, infant and young child feeding), as well as SMS reminders to highlight certain messages on antenatal care and nutrition. All products and trainings will be

provided free of charge. The households in the intervention group will also have the same agricultural intervention as the control group.

- b) Control group: All households will be provided with agricultural training (every 2 weeks on average) for free. In addition, households can also enrol for the following products on credit: compost booster, cook stoves, seeds (onions, maize, indigenous greens, beans), maize storage bags, drying tarps, trees, solar lights, fertilizer, actellic dust (insecticide), re-usable sanitary pads.

We anticipate recruiting 1200 (600 in each group) pregnant women into the study (see section 7.2 for sample size calculation); this is expected to yield a sufficiently large sample of children later in the study. Women will be recruited from 120 clusters (randomly assigned to intervention or control) that will be drawn from from Kimilili and Webuye districts in Bungoma County in Western Province of Kenya.

We anticipate recruiting 1,200 (600 in each group) pregnant women into the study (see section 11.2 for sample size calculation); this is expected to yield a sufficiently large sample of children later in the study. Women will be recruited from 120 clusters (randomly assigned to intervention or control) that will be drawn from from Kimilili and Webuye districts in Bungoma County in Western Province of Kenya.

The communities will be informed about the study in village meetings by CHVs and by conducting outreach within their catchment area to identify pregnant women. Pregnant women will then be screened by 1AF enumerators. During **screening**, a few questions on health status and pregnancy will be asked. If the woman is prior or equal to 20 weeks of gestation (according to last menstrual period), has no visible severe disease and no allergy to peanuts or milk products, and confirms anticipated residence in the area for the coming 30 months, written informed consent for her and her offspring will be sought from her. She will then be asked to provide a urine sample to confirm pregnancy and she will be enrolled if pregnancy is confirmed. Following the screening, 5 assessment rounds (baseline and 4 follow-up assessments during the intervention) will be conducted at the participant's homes (rounds 1-3) or at a central place (rounds 4 and 5) within walking distance from their homes (Figure 2). Assessment round 3 (immediately) after delivery will be conducted as home visits or clinic visits in case of delivery at a clinic. Details of assessment procedures for each round are illustrated in (Figure 3).

Round 1 (Enrolment, ≤ 20 wk of gestation):

On the day of enrolment the round 1 assessment will be done. As part of this, the following information will be collected: household demographics and characteristics, maternal education; knowledge, attitude and practices (KAP) of specific dietary and nutrition practices during pregnancy; individual dietary diversity; antenatal care; WASH practices; height, weight and mid-upper arm circumference; maternal haemoglobin concentration and malaria parasitaemia from a capillary blood sample. After round 1, participants randomly allocated to the intervention group will start receiving the intervention package.

Round 2 (Gestational age of 34 ± 1 wk):

In round 2, interview questions related to diet and nutrition KAP during pregnancy, dietary diversity, antenatal care, and WASH will be asked. Additionally, MUAC (mid-upper arm circumference) will be measured and a capillary blood sample for measurement of haemoglobin concentration, malaria parasitaemia and micronutrient status will be provided.

Round 3 (Within 24-48 hours after delivery):

The mother-child pair will be visited within 24-48 hours after delivery. The following information will be recorded: delivery date and time, delivery method, recent antenatal care, and early initiation of breastfeeding. The mother will be assessed for MUAC but no blood sampling will be conducted. For the newborn, head circumference, birth weight and birth length, and haemoglobin concentration (from a heelprick) will be measured.

Round 4 (At 6.5 mo ± 1 mo of age of offspring):

This assessment will be conducted when the child turns 6.5 months old. Breastfeeding and other infant and young child feeding indicators, child morbidity, maternal dietary diversity, postnatal care, and WASH information will be gathered. In mothers, MUAC and weight will be measured and haemoglobin concentration and malaria parasitaemia from a capillary sample will be assessed. In

children, length, weight and head circumference will be measured and a capillary blood sample for haemoglobin concentration, malaria parasitaemia and micronutrient status will be provided.

Round 5 (At 24 ± 1mo of age of offspring):

This assessment will be conducted when the child turns 24 months old. Questionnaire-based information on child feeding, child dietary diversity, child morbidity and WASH will be collected. As in round 4, child length, weight and head circumference will be measured and a fingerprick blood sample will be provided for the measurement of haemoglobin concentration, malaria parasitaemia, and micronutrient status. No maternal biomarkers will be collected at this point.

As part of the monthly visits to the participants' households, the CHV will also collect data on intervention adherence and recent morbidity.

[figure not shown]

Figure 2: Timing of assessment rounds for study 1.

[figure not shown]

Figure 3: Detailed procedures for each assessment round in study 1

(LMP: last menstrual period; GA: gestational age; ICD: informed consent document; MUAC: mid-upper arm circumference; Hb: haemoglobin; RDT: rapid diagnostic test (for malaria); HH: household; SES: socioeconomic status; KAP: knowledge, attitude and practice; ANC: antenatal care; WASH: water, sanitation and hygiene; MN: micronutrients; HC: head circumference; IYCF: infant and young child feeding)

The detailed procedures of study 1 are summarized in Table 3 below.

Table 3: Study 1 summary table of procedures and assessments

Study Periods	Screening		Intervention Period			
Visit/Round	0	1	2	3	4	5
Time (hour, day, week)	≤20 wk GA	≤20 wk GA	34±1wk GA	Delivery +48h	Infant 6.5±1 mo old	Infant 24±1 mo old
Randomisation of clusters (done prior to recruitment)						
Oral consent for screening questions	x					
Pregnancy and health status questions	x					
In- /exclusion criteria	x					
Written participant information and informed consent		x				
Pregnancy test		x				
Re-assessment of in- /exclusion criteria		x				
Household demographics/characteristics		x				
Maternal education		x				
Maternal anthropometry		x	x	x	x	
Child anthropometry				x	x	x
Capillary blood sampling in women		x	x		x	
Capillary blood sampling in children				x	x	x
Ante-/postnatal care		x	x	x	x	
Dietary and nutrition practices KAP, dietary diversity (pregnancy, lactation)		x	x		x	
WASH practices		x	x		x	x
Delivery information (incl. breastfeeding, birth weight and length)				x		
Breastfeeding and other IYCF indicators					x	x
Child dietary diversity					x	x
Child morbidity					x	x
Intervention adherence			x	x	x	x

Study 2:

General study design: Study 2 is a cluster-randomized, parallel-group, prospective, follow-up effectiveness study over a period of 2 years comparing 2 groups of children 6-35 months of age at recruitment:

- a) Intervention group: All selected households with children 6-35 months of age at recruitment will receive MNP (1 sachet every three days per child) and ORS along with zinc (20 mg/day) for treatment of acute diarrhoea. The households will also be provided with soap, chlorine solution, poultry (8 chickens at start of intervention), and seeds for red onion and indigenous greens (March 2018 and March 2019). The products will be accompanied by monthly nutrition and WASH trainings. The products and trainings will be provided free of charge. Additionally, all households will receive the agricultural package as in the control group.
- b) Control group: All households will be provided with agricultural training (every 2 weeks on

average) for free. In addition, households can also enrol for the following products on credit: compost booster, cook stoves, seeds (onions, maize, indigenous greens, beans), maize storage bags, drying tarps, trees, solar lights, fertilizer, actellic dust (insecticide), re-usable sanitary pads.

We anticipate recruiting 2,000 (1,000 in each group) children 6-35 months of age into the study (see section 7.2 for sample size calculation). Children will be recruited from 100 clusters (randomly assigned to intervention or control) that will be drawn from Lugari district in Kakamega County located in the Western Province of Kenya.

Questionnaire based and anthropometric data will be collected in **3 rounds** at a central place in walking distance from participant's homes one year apart from each other (Table 4). The following information will be collected in **round 1** (baseline assessment prior to the actual start of intervention distribution):

- Age
- Height and weight
- Household demographics/characteristics and caregiver's education
- Dietary diversity, breastfeeding and infant and young children feeding (IYCF) practices
- WASH practices
- Child morbidity

In **rounds 2 and 3**, information on dietary diversity, breastfeeding and IYCF practices, WASH practices and child morbidity will be collected again. Additionally, changes in adherence and coverage of the intervention package as well as unintended outcomes (e.g. reduction of exclusive breastfeeding due to premature introduction of complementary foods) will be assessed.

Table 4: Study 2 summary table of procedures and assessments

Study Periods	Intervention Period		
	1	2	3
Visit/Round	1	2	3
Time (hour, day, week)	Prior to start of intervention	1 year after start of intervention	2 years after start of intervention
Age (Date of birth)	x		
Anthropometry	x	x	x
Household demographics/characteristics	x		
Mother's/caregiver's education	x		
Dietary diversity, breastfeeding and child feeding practices	x	x	x
WASH practices	x	x	x
Child morbidity	x	x	x
Adherence to and coverage of intervention package		x	x

